**Design**

Open label cross-over pilot study to determine safety and efficacy of teduglutide in patients with ECF. Our planned sample size is 10 subjects randomized and treated with at least 1-dose of study drug .

IRB Study Number: 20170189  
Version Date: June 16, 2021  
PI: [name]

NCT02889393

The primary efficacy end point will be decrease in fistula volume by 20% from baseline 3-day average, as measured by the patient.

The secondary efficacy end points will be cessation of fistula output altogether and health-related quality of life questionnaire score as assessed by the questionnaires (see below) at time points Study Visit 5, 10, and 11 (3 months after end-of-treatment).

Subjects that complete both arms of the study who have a favorable (but incomplete) response and are deemed to be reliable (both as determined by the principal investigator) will be offered an open-label extension during which they will continue to receive teduglutide for up to another 12 months or permanent fistula closure, whichever occurs first.

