### **Enrollment within 2 months of signing consent**

Inclusion/Exclusion criteria

Vital signs measurements

Nutritional assessment

3-day average fistula output

Complete questionnaires (see additional documents):

1. ASCQ-Me Short Form v2.0 - Social Functioning Impact
2. ASCQ-Me v2.0 - Sleep Impact Short Form

IRB Study Number: 20170189  
Version Date: June 16, 2021  
PI: [name]

NCT02889393

3. Global Health Scale v1.2
4. PROMIS Scale v1.0 - GI Belly Pain
5. PROMIS Scale v1.0 - GI Diarrhea
6. PROMIS Scale v1.0 - GI Nausea and Vomiting
7. PROMIS SF v2.0 - Ability to Participate

Teaching of self-administration of medication

After study enrollment, the subject will be randomly assigned (by a computerized method, using the site 'www.sealedenvelope.com') to begin teduglutide treatment immediately or to continue standard of care (SOC) treatment. The randomization will be performed by a member of the study that is not involved in the informed consent process, and will be enclosed in sequentially numbered opaque envelopes. The envelopes will be given to the PI prior to the enrollment visit. At study visit 5 (day 56), the subject will then cross-over to the opposite treatment assignment. The half-life of teduglutide is 2-3 hours. During the period the subjects are on the "SOC only" treatment arm, the subjects will be given the option to replace some Study visits with Telephone Calls for their convenience. If study visits overlap due to the time window, either visit may be skipped or completed on the same day. Please see information below, and the Study schema.

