**Study Visit 1 or Telephone Call as applicable (Day 7) (+/- 3 days)**

Collect physical examination if during visit

Collect Vital Signs measurements if during visit

Monitor severe adverse events (SAE) and adverse events (AE)

Collect concomitant medication review

Collect Nutritional Assessment

3-day average fistula volume (3 days immediately preceding study visit) from the Diaries

Collect adjustment of medications and fluids if recorded

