**Study Visit 8 or Telephone Call as applicable (Day 84) (+/- 1 week)**

Collect physical examination if during visit

Collect Vital Signs measurements if during visit

Chemistry Panel (sodium, potassium, chloride, bicarbonate, blood urea nitrogen, creatinine glucose)

Liver Function tests (total bilirubin, direct bilirubin, alkalkine phosphatase, alanine aminotransferase, aspartate aminotransferase, lipase, amylase)

Plasma PK (Pharmacokinetics)

- Processed according to separate “Sample Processing Procedure”

IRB Study Number: 20170189  
Version Date: June 16, 2021  
PI: [name]

NCT02889393

Serum pregnancy test  
Monitor severe adverse events (SAE) and adverse events (AE)  
Collect Concomitant medication review  
Collect Nutritional Assessment  
3-day average fistula volume (3 days immediately preceding study visit)  
Collect adjustment of medications and fluids if recorded

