## **7) Biostatistical Analysis**

Because this is a pilot study enrolling only 10 subjects, no sample size or power calculation was performed. The primary endpoint (decrease in fistula volume by 20%) was chosen based on previous studies in a different population.

Continuous outcome variables that are normally distributed will be presented as mean  $\pm$  Standard Deviation (SD) while continuous outcome variables that are not normally distributed will be presented as median and interquartile range (IQR). In calculating the difference in fistula volume between baseline and final measures, a two-sample t-test for independent samples will be used. A p value of <0.05 will be considered significant.

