### **Procedures for Reporting Adverse Events**

Adverse events may be spontaneously reported, obtained through non-leading questioning, or noted during examination of a subject. Adverse events will be recorded from the signing of informed consent through the last dose of study drug. Serious adverse events will be recorded from the signing of informed consent through 30 days after the last dose of study drug.

At each visit, new AEs are recorded sequentially on the Adverse Event log. The AE term will note the diagnosis whenever possible, not the individual signs or symptoms (eg., myocardial infarction will be recorded rather than chest pain, elevated cardiac enzymes, and abnormal ECT). Also recorded are:

- Start and stop date and time
- Whether or not the event is continuing
- Frequency (intermittent, continuous)
- Intensity (mild, moderate, severe)
  - Mild: usually transient, requiring no special treatment and generally not interfering with usual daily activities
  - Moderate: usually ameliorated by simple therapeutic maneuvers and impairs usual activities
  - Severe: requires vigorous therapeutic intervention and interrupts usual activities. Hospitalization may or may not be required.
- Relationship to study drug (not related, related): identify relationship as “related” if a causal relationship between the investigational product and an AE is at least a reasonable possibility (i.e. the relationship cannot be ruled out).
- Whether or not the AE is serious (i.e. an SAE). If identified as an SAE, the AE will be reported as an SAE.
- Actions taken (none, study drug dose interrupted, study drug discontinued, other medication change, non-drug therapy, change in parenteral nutrition or IV fluids).
- Outcome (resolved, severity or frequency increased, ongoing, fatal). An individual AE receives only one outcome.

IRB Study Number: 20170189  
Version Date: June 16, 2021  
PI: [name]

NCT02889393

Adverse events not resolved at the end of treatment will be followed until resolution or until the AE is judged by the investigator to have stabilized.

✓

Laboratory values, blood pressure, ECG evaluations, and clinical findings at the scheduled physical examinations will be reported as AEs if they:

- Are considered clinically significant by the investigator
- Fulfill SAE criteria, and/or
- Cause subject discontinuation from the study

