**Appendix E Treatment Schema**

	Eligibility / Screening	Enrollment	Treatment							Cross-over
			Day 7 Study Visit 1 +/- 3 days	Day 14 Study Visit 2 or Telephone +/- 3 days	Day 21 Telephone Call 1 +/- 3 d	Day 28 Study Visit 3 +/- 1 week	Day 35 Telephone Call 2 +/- 3 days	Day 42 Study Visit 4 or Telephone +/- 1 week	Day 49 Telephone Call 3 +/- 3 d	Day 56 Study Visit 5 +/- 1 week
Informed Consent	X	X								
Inclusion and exclusion criteria	X	X								
Demographics	X									
Medical and surgical history	X									
Review prior and concomitant medications	X									
Complete Physical Exam A	X		X	X		X		X		X
Vital signs measurements B	X	X	X	X		X		X		X
Self-administration of medication and teaching if needed		X	X	X	X	X	X	X	X	X
IP Dispensation and Accountability		X	X	X		X		X		X
Chemistry panel	X					X				X
Liver function tests	X					X				X
Plasma PK*						X				X
Serum pregnancy test	X					X				X
ECG	X									
Monitor SAE/AE C			X	X	X	X	X	X	X	X
Concomitant medication review	X		X	X		X		X		x
Nutritional assessment D	X	X	X	X	X	X	X	X	X	X
3- day fistula output	X	X	X	X	X	X	X	X	X	X
Questionnaires		X								X

IRB Study Number: 20170189  
 Version Date: June 16, 2021  
 PI: [name]

NCT02889393

	Treatment							End-of-Treatment	Long-Term Follow-up
	Day 63 Study Visit 6 or Telephone +/- 1 week	Day 70 Study Visit 7 or Telephone +/- 1 week	Day 77 Telephone Call 4 ± 3 d	Day 84 Study Visit 8 ± 1 week	Day 91 Telephone Call 5 ± 3 d	Day 98 Study Visit 9 or Telephone +/- 1 week	Day 105 Telephone Call 6 ± 3 d	Day 112 Study Visit 10 ±1 week	Study Visit 11 (3 months after EOT) -2wks to +3 mos.
Informed Consent									
Inclusion and exclusion criteria									
Demographics									
Medical and surgical history									
Review prior and concomitant medications									
Complete Physical Exam A	X	X		X		X		X	
Vital signs measurements B	X	X		X		X		X	
Self-administration of medication and teaching if needed	X	X	X	X	X	X	X		
IP Dispensation and Accountability	X	X		X		X		X E	
Chemistry panel				X				X	X
Liver function tests				X				X	X
Plasma PK*				X				X	X
Serum pregnancy test				X				X	X
Monitor SAE/AE C	X	X	X	X	X	X	X	X	X
Concomitant medication review	X	X		X		X		X	X
Nutritional assessment D	X	X	X	X	X	X	X	X	X
3- day fistula output	X	X	X	X	X	X	X	X	X
Questionnaires								X	X

IRB Study Number: 20170189  
 Version Date: June 16, 2021  
 PI: [name]

NCT02889393

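### Calls may replace visits only on SOC, so adverse events found by examination or vital signs may be sought more often on teduglutide; the Day 84 visit and the AE window need reconciling

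*Combined protocol and SAP*

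**What the plan says.** The Enrollment part of Section 5 states that, while on SOC only, "the subjects will be given the option to replace some Study visits with Telephone Calls for their convenience". Neither that section nor the visit list limits how many visits may be replaced.

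The visit-list headings allow a call at Visits 1, 2, 4, 6, 7, 8 and 9. Visits 3, 5 and 10 carry no such option. AEs, medication review, nutrition and 3-day output are listed at every visit-or-call contact. Examination and vital signs are conditional on an actual visit at Visits 1, 2, 4, 6 and 8. At Visits 7 and 9 they are listed without that condition, although a call is allowed.

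Two headings disagree with Appendix E:
- Day 84 is "Study Visit 8 or Telephone Call as applicable (Day 84) (+/- 1 week" in the visit list but "Day 84 Study Visit 8 ± 1 week" in the schema. The visit list gives chemistry, liver tests, PK and the pregnancy test there without condition.
- Day 7 is "Study Visit 1 or Telephone Call as applicable (Day 7) (+/- 3 days" in the visit list, while the schema offers no call.

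On AEs, Section 9 says "Laboratory values, blood pressure, ECG evaluations, and clinical findings at the scheduled physical examinations will be reported as AEs if they" meet any of three criteria, the first being clinical significance in the investigator's judgement. It records AEs from consent to the last dose of study drug. Footnote C to Appendix E follows AEs to Visit 11.

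**The concern.** Safety is the first-named objective, and SOC is the only comparator within the study. If contact mode depends on treatment, so does the chance of finding anything that needs hands, a stethoscope, a cuff or a scale. Fluid overload shows the problem. It has the highest rate among the specific risks in Section 8 (13.3%), and the signs listed in Section 6 include rales, pitting edema and weight change. By telephone these rest on self-report or cannot be observed. With equal true risk, more in-person contacts on drug would yield more recorded AEs on drug.

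The Day 84 conflict adds a laboratory version of the problem in one sequence only. The conflict over the AE window could remove non-serious AEs from the SOC period of subjects treated first.

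**Working it through.** The plan has no figure to reproduce: "no sample size or power calculation was performed". The check is a count from the visit list and Appendix E, plus one illustration.

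| Visit (day) | Call allowed, visit list | Call allowed, Appendix E | Examination and vital signs in visit list |
|---|---|---|---|
| 1 (7) | yes | no | only if a visit |
| 2 (14) | yes | yes | only if a visit |
| 3 (28) | no | no | required |
| 4 (42) | yes | yes | only if a visit |
| 5 (56) | no | no | required |
| 6 (63) | yes | yes | only if a visit |
| 7 (70) | yes | yes | unconditional |
| 8 (84) | yes | no | only if a visit |
| 9 (98) | yes | yes | unconditional |
| 10 (112) | no | no | required |

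**Step 1: floor of in-person visits per SOC period.** Five visits minus those that may be calls.
- Visit list: period 1, 5 − 3 = 2; period 2, 5 − 4 = 1.
- Appendix E: period 1, 5 − 2 = 3; period 2, 5 − 3 = 2.
- On teduglutide: 5 in either period.

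**Step 2: totals.** The Design section says "Our planned sample size is 10 subjects randomized and treated with at least 1-dose of study drug" but gives no allocation ratio. I assume 10 completers split 5:5, with 4:6 to 6:4 as the range (SOC-first : teduglutide-first).
- Teduglutide: 10 × 5 = 50.
- SOC, visit list: 5 × 2 + 5 × 1 = 15 (range 4 × 2 + 6 × 1 = 14 to 6 × 2 + 4 × 1 = 16).
- SOC, Appendix E: 5 × 3 + 5 × 2 = 25 (range 4 × 3 + 6 × 2 = 24 to 6 × 3 + 4 × 2 = 26).
- If the unconditional listing at Visits 7 and 9 means those examinations are done regardless, the visit-list floor of examinations becomes 5 × 2 + 5 × 3 = 25.

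**Step 3: what unequal looking can do at equal true risk.** Let q be the chance of a visit-only finding at one visit (assumed, since the documents give none). The chance of at least one finding in n visits is 1 − (1 − q)^n.

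| q | n = 5 | n = 3 | n = 2 | n = 1 |
|---|---|---|---|---|
| 0.05 | 22.6% | 14.3% | 9.8% | 5.0% |
| 0.20 | 67.2% | 48.8% | 36.0% | 20.0% |

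**Step 4: mid-period laboratory draws.** Day 28 is in person in both sequences, so period 1 has no gap. At Day 84 the draw is at risk only in teduglutide-first subjects, and only if a call is taken to cancel it. Draws on teduglutide: 10. Draws on SOC: 10 if the schema or the unconditional listing is followed, and as few as 5 (4 to 6 by split) if not.

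**Step 5: AE window.** In the cross-over, a teduglutide-first subject takes the last dose at about Day 56 and is on SOC from Day 56 to Day 112, which is 112 − 56 = 56 days. Under Section 9, non-serious AEs in those days fall after recording stops, unless a later extension moves the last dose. Under footnote C they are recorded.

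**The case against.** Four arguments on the other side have weight.

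- **Uptake is unknown.** Replacement is optional and covers only some visits, so 15 and 25 are floors and not forecasts. This stands. A reader might infer that AEs will be higher on teduglutide because of visit frequency. The documents support only that they may be.
- **No safety comparison is planned.** Section 7 describes summaries and a test on fistula volume. AEs are asked about at every contact, so AEs obtained by questioning are not affected by this asymmetry. This stands, and it limits the point to a side-by-side AE table, which a study with this objective is likely to produce.
- **The laboratory gap is narrow.** Only Day 84, only one sequence, and only on one reading of a list that states the tests without condition. This also stands. What remains is a contradiction that site staff cannot resolve from the text.
- **Fewer SOC visits are a deliberate convenience in a 10-subject pilot.** That is reasonable, and the remedy below keeps nearly all of it.

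A reader might also infer that the primary endpoint is compromised, on the view that output is seen in the diary on drug and reported verbally on SOC. The documents do not support this. At Days 7 and 14 output comes from the diaries whether the contact is a visit or a call. Three scheduled calls per period collect it in both conditions. The end-of-period values at Days 56 and 112 are taken at in-person visits in both sequences.

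**Conclusion.** The point holds as a modest one. Following the plan can give unequal ascertainment of AEs found by examination or vital signs: 50 in-person visits on teduglutide against a floor of 15 (visit list) or 25 (Appendix E) on SOC. This assumes 10 completers, full attendance, a 5:5 split and maximal replacement. Any resulting bias runs against the drug. Laboratory findings are affected only through the unresolved Day 84 conflict, in teduglutide-first subjects.

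The AE-window conflict matters to the same comparison. If recording stops at the last dose, non-serious AEs on SOC are lost in those same subjects, which again makes SOC look safer. The fistula-volume endpoint is not part of this finding.

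**What to change.** 1. Reconcile the Visit 8 entry in the visit list with Appendix E, so that the Day 84 tests are collected in both sequences, as those at Visit 3 are. Reconcile the Visit 1 heading with Appendix E as well, and state whether a call at Visit 7 or 9 removes the examination and vital signs.
2. Record the mode of each contact. In any teduglutide-versus-SOC safety table, compare AEs elicited by questioning across all contacts. Use examination, vital-sign and laboratory findings only from Visits 3, 5, 8 and 10, and list findings from other visits separately so that no safety observation is lost. Visit 8 can serve as a matched visit only once item 1 is settled.
3. Reconcile the AE recording window in Section 9 with footnote C to Appendix E, so that it is clear whether non-serious AEs in the SOC period of teduglutide-first subjects are recorded.

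The cost is slightly less convenience at Day 84 for teduglutide-first subjects, one extra field for contact mode, and a little more table work. The other telephone options can stay.

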**Study Visit 1 or Telephone Call as applicable (Day 7) (+/- 3 days)**

Collect physical examination if during visit

Collect Vital Signs measurements if during visit

Monitor severe adverse events (SAE) and adverse events (AE)

Collect concomitant medication review

Collect Nutritional Assessment

3-day average fistula volume (3 days immediately preceding study visit) from the Diaries

Collect adjustment of medications and fluids if recorded

**Study Visit 2 or Telephone Call as applicable (Day 14) (+/- 3 days)**

Collect physical examination if during visit

Collect Vital Signs measurements if during visit

Monitor severe adverse events (SAE) and adverse events (AE)

Collect Concomitant medication review

Collect Nutritional Assessment

3-day average fistula volume (3 days immediately preceding study visit) from the Diaries

Collect adjustment of medications and fluids if recorded

**Telephone Call 1 (Day 21) (+/- 3 days)**

Monitor severe adverse events (SAE) and adverse events (AE)

Nutritional Assessment

3-day average fistula volume (3 days immediately preceding telephone call)

Adjustment of medications and fluids if necessary

**Study Visit 3 (Day 28) (+/- 1 week)**

IRB Study Number: 20170189  
Version Date: June 16, 2021  
PI: [name]

NCT02889393

Collect physical examination  
Collect Vital Signs measurements  
Chemistry Panel (sodium, potassium, chloride, bicarbonate, blood urea nitrogen, creatinine glucose)  
Liver Function tests (total bilirubin, direct bilirubin, alkalkine phosphatase, alanine aminotransferase, aspartate aminotransferase, lipase, amylase)  
Plasma PK (Pharmacokinetics)

- Processed according to separate “Sample Processing Procedure”

Serum pregnancy test  
Monitor severe adverse events (SAE) and adverse events (AE)  
Collect Concomitant medication review  
Collect Nutritional Assessment  
3-day average fistula volume (3 days immediately preceding study visit)  
Collect adjustment of medications and fluids if recorded

**Telephone Call 2 (Day 35) (+/- 3 days)**

Monitor severe adverse events (SAE) and adverse events (AE)  
Nutritional Assessment  
3-day average fistula volume (3 days immediately preceding telephone call)  
Adjustment of medications and fluids if necessary

**Study Visit 4 or Telephone Call as applicable (Day 42) (+/- 1 week)**

Collect physical examination if during visit  
Collect Vital Signs measurements if during visit  
Monitor severe adverse events (SAE) and adverse events (AE)  
Collect Concomitant medication review  
Collect Nutritional Assessment  
3-day average fistula volume (3 days immediately preceding study visit)  
Collect adjustment of medications and fluids if recorded

**Telephone Call 3 (Day 49) (+/- 3 days)**

Monitor severe adverse events (SAE) and adverse events (AE)  
Nutritional Assessment  
3-day average fistula volume (3 days immediately preceding telephone call)  
Adjustment of medications and fluids if necessary

**Study Visit 5, Cross-over, (Day 56) (+/- 1 week)**

Collect physical examination  
Collect Vital Signs measurements  
Chemistry Panel (sodium, potassium, chloride, bicarbonate, blood urea nitrogen, creatinine glucose)  
Liver Function tests (total bilirubin, direct bilirubin, alkalkine phosphatase, alanine aminotransferase, aspartate aminotransferase, lipase, amylase)

IRB Study Number: 20170189  
Version Date: June 16, 2021  
PI: [name]

NCT02889393

Plasma PK (Pharmacokinetics)

- Processed according to separate “Sample Processing Procedure”

Serum pregnancy test

Monitor severe adverse events (SAE) and adverse events (AE)

Collect Concomitant medication review

Collect Nutritional Assessment

3-day average fistula volume (3 days immediately preceding study visit)

Collect adjustment of medications and fluids if recorded

Fistula closure (y/n)

Complete Questionnaires (see additional documents)

**Study Visit 6 or Telephone Call as applicable (Day 63) (+/- 1 week)**

Collect physical examination if during visit

Collect Vital Signs measurements if during visit

Monitor severe adverse events (SAE) and adverse events (AE)

Collect Concomitant medication review

Collect Nutritional Assessment

3-day average fistula volume (3 days immediately preceding study visit)

Collect adjustment of medications and fluids if recorded

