**Study Visit 7 or Telephone Call as applicable (Day 70) (+/- 1 week)**

Collect physical examination

Collect Vital Signs measurements

Monitor severe adverse events (SAE) and adverse events (AE)

Collect Concomitant medication review

Collect Nutritional Assessment

3-day average fistula volume (3 days immediately preceding study visit)

Collect adjustment of medications and fluids if recorded

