**Telephone Call 4 (Day 77) (+/- 3 days)**

Monitor severe adverse events (SAE) and adverse events (AE)

Nutritional Assessment

3-day average fistula volume (3 days immediately preceding telephone call)

Adjustment of medications and fluids if necessary

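### Patients who start on standard of care get wider visit windows in their first weeks on teduglutide (first contact up to 14 days after first dose, against 10), because windows follow the study period rather than the start of drug

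*Combined protocol and SAP*

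**What the plan says.** All references are to the combined protocol and SAP.

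- **Start of drug.** The enrollment section has one group begin teduglutide at once and the other continue SOC, with the switch at Visit 5. That visit is headed "Study Visit 5, Cross-over, (Day 56) (+/- 1 week".
- **First on-drug contacts, teduglutide-first.** "Study Visit 1 or Telephone Call as applicable (Day 7) (+/- 3 days" and "Study Visit 2 or Telephone Call as applicable (Day 14) (+/- 3 days".
- **First on-drug contacts, SOC-first.** "Study Visit 6 or Telephone Call as applicable (Day 63) (+/- 1 week" and "Study Visit 7 or Telephone Call as applicable (Day 70) (+/- 1 week". Appendix E repeats the one-week windows, so this is not a slip in one heading. The next contact is "Telephone Call 4 (Day 77) (+/- 3 days".
- **Overlap rule**, enrollment section: "If study visits overlap due to the time window, either visit may be skipped or completed on the same day".
- **What the contacts are for.** The Data Fields section has fluid and volume status checked at study visits and by the patient's own report on calls. Section 8 (Risks to Subjects) describes weekly assessments at which parenteral nutrition volume is cut if fluid overload is suspected. It reports fluid overload in 13.3% of teduglutide-treated patients in pooled Phase III studies.
- **Timing by treatment.** Drug Administration sets 8 weeks of dosing. Section 8 places laboratory tests before drug, at week 4, after the 8 weeks, and at long-term follow-up.

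**The concern.** Both sequences receive the same drug at the same dose for the same time, so the early on-drug checks should be equally close to first dose. They are not, because the narrow windows belong to the first period. SOC-first patients have them while off drug and move to wider windows as they start teduglutide. No reason is given for the difference.

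Since fluid status is checked at these contacts, a first contact at 14 days or later does not deliver the weekly assessment that Section 8 describes. A second issue follows from the running study-day count. The visit headings do not say whether second-period windows move with the actual cross-over date. If they do not, time on drug at the mid-treatment laboratory tests and at the end-of-period visit varies more for SOC-first patients. The end-of-period visit also carries fistula volume, closure and the questionnaires.

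**Working it through.** The plan states no figure for time to first on-drug contact, so there is none to reproduce. The check is calendar arithmetic on the headings.

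**Assumptions.** First dose is on the Visit 5 date (SOC-first) or Day 0 (teduglutide-first; a Day 1 start would shorten that sequence's gap by one day). Except where stated, windows are read as written, in study days.

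**Windows** (nominal day ± width):

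| Contact | Study days |
|---|---|
| Visit 1 | 4–10 |
| Visit 2 | 11–17 |
| Visit 3 | 21–35 |
| Call 3 | 46–52 |
| Visit 5 | 49–63 |
| Visit 6 | 56–70 |
| Visit 7 | 63–77 |
| Call 4 | 74–80 |
| Visit 8 | 77–91 |
| Visit 10 | 105–119 |

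**Latest first contact = last day of window − day of first dose.**

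- Teduglutide-first: 10 − 0 = 10 days. Visits 1 and 2 do not overlap, so the overlap rule does not reach them.
- SOC-first, Visit 6 held, by day of cross-over:
  - Day 56: 70 − 56 = 14 days
  - Day 49: 70 − 49 = 21 days
  - Day 60: 70 − 60 = 10 days
  - Day 63: 70 − 63 = 7 days

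The 14 days needs only an on-time cross-over and a late but compliant Visit 6. The 21 days also needs the study-day reading and Call 3 ("Telephone Call 3 (Day 49) (+/- 3 days") made by Day 49. If Call 3 falls on Days 50–52, it is itself a contact 1 to 3 days after first dose. A late cross-over shortens the gap.

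**Overlap rule.** Visit 6 shares Days 56–63 with Visit 5 and Days 63–70 with Visit 7. If Visit 6 is skipped, or combined with Visit 5, after a Day-56 cross-over, the next contact may be Visit 7 on Day 77: 77 − 56 = 21 days. After a Day-49 cross-over, the loosest reading gives 77 − 49 = 28 days. Both need Call 4 made no earlier than Day 77.

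**Laboratory tests and end of period, days after first dose, study-day reading.**

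- Visit 8, SOC-first: 77 − 63 = 14 to 91 − 49 = 42. Visit 3, teduglutide-first: 21 to 35.
- Visit 10, SOC-first: 105 − 63 = 42 to 119 − 49 = 70. Visit 5, teduglutide-first: 49 to 63.
- With cross-over exactly on Day 56, Visit 8 falls at 77 − 56 = 21 to 91 − 56 = 35, and Visit 10 at 105 − 56 = 49 to 119 − 56 = 63. The sequences then agree, so this part comes entirely from the missing anchor.

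**The case against.** The strongest reply is that these are stacked permissions in a 10-subject pilot, not the plan. Planned spacing is 7 days in both sequences. Section 8 speaks of weekly assessments, and Drug Administration refers to weekly visits in its source-document hierarchy, so a long silence would go against stated intent. SOC-first patients have an examination, vital signs, chemistry and liver tests at Visit 5 as drug starts. Adverse events may be reported spontaneously, and patients on parenteral nutrition have laboratory tests in routine care. One-week windows also apply to Visits 3, 4 and 5. Most of this stands and keeps the point minor. It does not remove the 14-day case: the stated weekly intent does not narrow the Visit 6 window, and checks made at the start of drug cannot show the effects of later doses.

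A reader might infer more than the documents support:

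- **A 28-day gap as a plain consequence of the plan.** It requires that any two visits whose permitted ranges touch may be reduced to one, with the survivor placed outside the shared days. The same-day alternative in the rule suggests visits that actually collide. On that reading, if Visits 6 and 7 collide after a Day-49 cross-over, the survivor falls by Day 70, which is 21 days.
- **That nothing ties the second period to treatment time.** The 8 weeks of dosing and the week-4 laboratory tests do. The fault is that headings and treatment-time statements can disagree, with no rule on which governs.
- **That three days is the sponsor's declared safety standard.** The protocol never says so; it is only the width used for Visits 1 and 2.
- **That the reported obstruction onset from 6 days shows harm.** A contact on Days 4–10 may also come after Day 6, so this does not separate 10 from 14 days.
- **A rate of late contacts.** Any rate needs an assumed spread of visit dates, which the documents do not give.

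**Conclusion.** The asymmetry is real and minor. From the headings and Appendix E, with cross-over on schedule, SOC-first patients may have their first on-drug contact 14 days after first dose, against at most 10 for teduglutide-first patients. This rests on drug starting on the Visit 5 date and on Day 0 respectively.

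The 21-day figure for an early cross-over, and the 14–42-day laboratory and 42–70-day end-of-period ranges, rest further on windows fixed to study day. The headings suggest that reading, but the week-4 and 8-week statements pull against it. Anything added by the overlap rule depends on how overlap is understood. The documents do not support a claim that patients would be left unmonitored, or any estimate of how many would have a late first contact.

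**What to change.** Make two changes together, in the headings and in Appendix E:

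1. Count Visits 6–10 and Calls 4–6 from the actual cross-over date.
2. Give Visits 6 and 7 the ±3-day window of Visits 1 and 2.

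Neither is enough alone. Re-anchoring only leaves 7 + 7 = 14 days (14 + 7 = 21 if Visit 6 is skipped). Narrowing only, with windows still on study days, leaves 66 − 49 = 17 days. Together they put Visit 6 at 4–10 days and Visit 7 at 11–17 days after cross-over. First contact is capped at 7 + 3 = 10 days, and neither visit overlaps Visit 5, Visit 8 or the other, so the overlap rule no longer reaches them. Mid-treatment laboratory tests then fall at 21–35 days and the end-of-period visit at 49–63 days in both sequences.

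The cost is text edits, slightly tighter windows for two contacts and possibly a few more deviations; no visits are added. Patients in their SOC period keep the telephone option. The change does not secure strictly weekly contact later on. If the intervening visit is skipped or an end-of-period visit is held late, longer gaps remain possible: a call at 18 days followed by a visit at 35 leaves 17 days in either sequence.
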